12. ASSESSMENT OF SAFETY

12.1. Adverse Events and Serious Adverse Events

12.1.1. Definitions of Adverse Events

12.1.1.1. Adverse Event

An AE is defined as any untoward medical occurrence associated with the use of the investigational product in humans, whether or not considered related to investigational product. An AE (also referred to as an adverse experience) can be any unfavorable and unintended sign (eg, an abnormal laboratory finding), symptom, or disease temporally associated with any use of the investigational product, without any judgment about causality and irrespective of route of administration, formulation, or dose, including an overdose.

AEs include, but are not limited to: (1) a worsening or change in nature, severity, or frequency of condition(s) present at the start of the study; (2) subject deterioration due to primary illness; (3) intercurrent illness; and (4) drug interaction.

Subjects should be questioned in a general way, without leading the subject or asking about the occurrence of any specific symptom. The Investigator should attempt to establish a diagnosis of the event based on signs, symptoms, and/or other clinical information. The diagnosis and not the individual signs/symptoms should be documented as the AE. For example, if the underlying disease process is a stroke, it would not be appropriate to record the AE by describing the

symptoms “sudden numbness, dizziness, and difficulty speaking.” The AE medical term of “stroke or cerebrovascular accident” should be recorded as it more accurately describes the AE.

12.1.1.2. Serious Adverse Event

An AE is considered “serious” if, in the view of either the Investigator or Sponsor, it results in any of the following outcomes:

- Death
- Is immediately life threatening.
- Requires in-subject hospitalization or prolongation of existing hospitalization.
- Results in persistent or significant disability or incapacity.
- Results in a congenital abnormality or birth defect.
- Is an important medical event that may jeopardize the subject or may require medical intervention to prevent one of the outcomes listed above.

Events not considered to be SAEs are hospitalizations for:

- Routine monitoring of the studied indication and not associated with any deterioration in condition or AE.
- Elective treatment for a pre-existing condition that did not worsen.
- Respite care or observation when there is no AE associated with the hospitalization.

12.1.1.3. Treatment-Emergent Adverse Event

A treatment-emergent AE (TEAE) is any event not present prior to the initiation of the investigational product or any event already present that worsens in either intensity or frequency following exposure to the investigational product.

12.1.2. Relationship to Investigational Product

The Investigator will document her/his opinion of the relationship of the AE to treatment with the investigational product using the criteria outlined in [Table 8](#). An AE for which there is a ‘reasonable possibility’ that the investigational product caused the AE is otherwise referred to as suspected adverse reaction (SAR). “Reasonable possibility” means there is evidence to suggest a causal relationship between the investigational product and the AE.

If the relationship between the AE/serious adverse event (SAE) and the investigational product is determined to be “possible” or “probable” the event will be considered to be related to the investigational product for the purposes of expedited regulatory reporting.

Table 8: Relationship of Adverse Events to Investigational Product

Relationship	Description
Definite	A reaction that follows a reasonable temporal sequence from administration of the investigational product or in which the investigational product level has been established in body fluids or tissue; that follows a known or expected response pattern to the suspected investigational product; and that is confirmed by improvement on stopping or reducing the dosage of the investigational product, and reappearance of the reaction on repeated exposure.
Probable	A reaction that follows a reasonable temporal sequence from administration of the investigational product; that follows a known or expected response pattern to the suspected investigational product; that is confirmed by stopping or reducing the dosage of the investigational product; and that could not be reasonably explained by the known characteristics of the subject's clinical state.
Possible	A reaction that follows a reasonable temporal sequence from administration of the investigational product; that follows a known or expected response pattern to the suspected investigational product; but that could readily be produced by a number of other factors.
Unlikely	A reaction that does not follow a reasonable temporal sequence from administration of the investigational product; that does not follow a known or suspected response pattern to the suspected investigational product; and that could reasonably be explained by known characteristics of the subject's clinical state.
Not Related	Any event that does not meet the above criteria.

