12.1.5. Suspected Liver-Related Clinical Outcome Events

Specified liver-related clinical outcome events may, by definition (see [Section 12.1.1.2](#)) qualify as SAEs. The Sponsor must be notified of any SAEs within 24 hours of the site becoming aware of the event (see [Section 12.1.4.2](#)). The Sponsor is responsible for regulatory reporting of SAEs, including expeditious reporting of SUSARs, which are defined as SAEs that are considered related (definitely, probably, or possibly related) to the investigational product and considered unexpected as defined in the IB.

Given that the liver-related clinical outcome events could also meet the criteria of a SUSAR, which would necessitate unblinding for expedited reporting, the Sponsor will not expeditiously report suspected liver-related clinical outcome events in order to retain the study blind and preserve the integrity of the clinical outcomes endpoint. These events will be selected as a “study event” on the Adverse Event CRF and will be submitted for adjudication to the Hepatic Outcomes Committee as described in [Section 13.4](#).

The Sponsor will consider the following list of clinical outcome events (MedDRA preferred terms) to be disease related and exempt from expeditious regulatory reporting, but will continue to report them in a non-expeditious manner: death, end-stage liver disease (preferred term: chronic hepatic failure), liver transplant (preferred term: liver transplant), HCC (preferred term: hepatocellular carcinoma), variceal bleeding (preferred term: gastroesophageal variceal haemorrhage), hepatic encephalopathy (preferred term: hepatic encephalopathy), spontaneous bacterial peritonitis (preferred term: peritonitis bacterial), ascites (preferred term: ascites), and histological progression to cirrhosis (preferred term: hepatic cirrhosis).

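### Table 8 makes a known or expected response pattern a condition of every related grade, so a reaction of a new type is graded Not Related by the Investigator whatever its timing or behaviour on stopping

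*Protocol*

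**What the plan says.** Section 12.1.2 has the Investigator record an opinion of the "relationship of the AE to treatment with the investigational product using the criteria outlined in" Table 8. The pattern clause appears in all three related grades:

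- Definite: a reaction "that follows a known or expected response pattern to the suspected investigational product; and that is confirmed by improvement on stopping". Improvement after a dose reduction also counts, and the reaction must come back on re-exposure.
- Probable: a reaction "that follows a known or expected response pattern to the suspected investigational product; that is confirmed by stopping or reducing the dosage", and not reasonably explained by the subject's clinical state.
- Possible: a reaction "that follows a known or expected response pattern to the suspected investigational product; but that could readily be produced", the rival source being various other causes.

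Unlikely starts from the opposite timing: "A reaction that does not follow a reasonable temporal sequence from administration of the investigational product". It also requires the absence of a known or suspected pattern and the presence of another explanation. Not Related is the remainder: "Any event that does not meet the above criteria".

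The text above the table uses a different standard. A suspected adverse reaction is one with a reasonable possibility of causation, which "means there is evidence to suggest a causal relationship between the investigational product and the AE". That section then counts only Possible and Probable as related for expedited reporting. Section 12.1.5 defines SUSARs as "SAEs that are considered related (definitely, probably, or possibly related) to the investigational product and considered unexpected as defined in the IB".

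**The concern.** The clause sits in each related grade as a condition, with no alternative to it. The only alternative offered, in Definite, is between timing and a measured drug level. An event with no recognised pattern therefore cannot be graded related, however strong the other evidence. If it is well timed it cannot be Unlikely either, so it ends one step lower, below an event with poor timing and another explanation.

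Several parts of the protocol use the relationship grade:

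- Section 13.2.1 tabulates treatment-emergent events by relationship.
- Section 12.1.7 lifts the 24-hour reporting rule for serious events more than 30 days after stopping product when they are not considered related.
- Section 12.1.8 ties follow-up after the final visit to a possible, probable or definite grade, or to other clinical significance.
- Section 12.1.5 makes relatedness one of the two conditions for a SUSAR.

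The wording is used by investigators at about 170 sites over an estimated 10 years, and a statistical analysis plan cannot repair a grade after it has been recorded.

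**Working it through.** The protocol gives no figure to reproduce. The check is whether any route through Table 8 leads a new-type reaction to a related grade.

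**Inputs.** Seven yes/no features, all taken from Table 8: reasonable timing (T), drug level established in fluid or tissue (L), known or expected pattern (K), improvement on stopping or reducing (D), reappearance on re-exposure (R), explained by the clinical state (X), readily produced by other factors (O).

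**Rule as written, applied in order:**

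- Definite: (T or L) and K and D and R
- Probable: T and K and D and not X
- Possible: T and K and O
- Unlikely: not T and not K and X
- Not Related: everything else

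**Results with K = no:**

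| Fixed features | Combinations | Grade as written |
|---|---|---|
| T = yes | 2^5 = 32 | Not Related 32 |
| T = yes, D = yes | 2^4 = 16 | Not Related 16 |
| T = yes, D = yes, R = yes | 2^3 = 8 | Not Related 8 |
| T either way | 2^6 = 64 | Not Related 48, Unlikely 16 |

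No related grade is reachable without K. The counts describe the logic of the table. They are not frequencies of events.

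**Comparison with K as the only change.** Take T = yes, D = yes and X = no, with K = no: 2^3 = 8 combinations. As written, all 8 are Not Related. With K removed as a condition from Definite, Probable and Possible, 4 are Definite and 4 are Probable. The pattern clause alone decides the grade.

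**A default that stays too wide.** With K removed, T = yes and D = yes (X free, 16 combinations), the grades are Definite 8, Probable 4, Possible 2 and Not Related 2. Deleting the clause is therefore not quite enough while Not Related remains the catch-all.

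**The texts side by side.** Improvement on stopping and return on re-exposure are evidence suggesting causation, so the text of Section 12.1.2 makes the event a suspected adverse reaction. Table 8, in the same section, makes it Not Related. Both cannot be followed. Under Section 12.1.5 the event must be related and also unexpected per the Investigator's Brochure. On the Investigator's grade, a reaction of a truly new type meets the second condition and cannot meet the first.

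**A smaller mismatch.** Section 12.1.2 omits Definite from the grades treated as related for expedited reporting. Sections 12.1.5 and 12.1.8 include it.

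**The case against.** A reader might infer that new toxicities vanish from expedited reporting and from the safety data. The documents do not support that.

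- Section 12.1.4.2 has the Sponsor assess causality as well, and nothing shown ties the Sponsor to Table 8. Section 12.1.5 speaks of events considered related without saying by whom, so a Sponsor judgement can make an event a SUSAR.
- All adverse events are recorded whether or not thought related (12.1.4.1). All serious events must be reported to the Sponsor (12.1.4.2), and those within 30 days of stopping product go within 24 hours regardless of relationship (12.1.7).
- Overall incidence by treatment group, and the tables of serious events and of events leading to discontinuation, do not depend on the grade (13.2.1). With 1:1 placebo control, an excess in one arm shows without any causality judgement.
- The Data Monitoring Committee sees serious-event narratives, a cumulative list of serious events and summaries by masked treatment column, and may unblind (13.3). Suspected drug-related hepatic injury, suspected major cardiovascular events and all deaths are adjudicated (13.4).

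It is also fair to say that a known or expected pattern and expectedness per the Investigator's Brochure are different ideas. An event can fit the drug's pharmacology yet be unlisted, or be a more severe or specific form of a listed effect, and so be both related and unexpected. The SUSAR conditions collide only for reactions of a new type.

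Finally, the wording is from the Version 3.1 body. Version 4 (10 May 2017) lists a Table 8 of the same title, but its text is not in the part at hand.

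All of this stands and limits the consequence. It does not cure the table. No separate Sponsor scale or override rule appears in the text shown, and no second causality assessment is described for non-serious events.

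**Conclusion.** The defect holds as a matter of wording. In Version 3.1, a well-timed reaction of a new type is graded Not Related by the Investigator in every combination of the other features, contrary to the standard stated in the same section. The damage is confined to that grade and what relies on it: the by-relationship tables, the 24-hour rule for late serious events, post-study follow-up of related events, and the Investigator's contribution to SUSAR identification. Capture of the event, comparison between arms and the primary analysis are untouched.

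I rate it moderate. This assumes that investigators apply Table 8 as instructed. One who relies on the reasonable-possibility sentence instead would grade differently, which is itself a source of inconsistency between sites. Whether the point applies to Version 4 depends on wording not shown.

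**What to change.** In Table 8:

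- List the response pattern as supporting evidence for Definite, Probable and Possible, not as a necessary condition.
- Define Possible as a reasonable temporal sequence with a reasonable possibility of causation, to match the text of Section 12.1.2.
- Give Not Related a positive definition, so that it no longer collects unclassified events.

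In Section 12.1.2, add Definite to the grades treated as related for expedited reporting, so that it agrees with Section 12.1.5. Check first whether Version 4's Table 8 keeps the present wording.

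The cost is the wording of one table and one sentence, with a memo to sites. Somewhat more events will be graded Possible, and there will be some more expedited reports.

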12.1.3. Recording Adverse Event Severity

AEs must be graded for severity (ie, intensity). A severity category of mild, moderate, or severe, as defined in Table 9, must be entered on the AE CRF. It should be noted that the term "severe" used to grade intensity is not synonymous with the term "serious." The assessment of severity is made regardless of investigational product relationship or of the seriousness of the AE.

Table 9: Severity of Adverse Events

Grade	Clinical Description of Severity
1 = Mild	Causing no limitation of usual activities; the subject may experience slight discomfort.
2 = Moderate	Causing some limitation of usual activities; the subject may experience annoying discomfort.
3 = Severe	Causing inability to carry out usual activities; the subject may experience intolerable discomfort or pain.

12.1.4. Reporting of Adverse Events and Serious Adverse Events

12.1.4.1. Reporting of Adverse Events

AE data will be collected from the time that signed informed consent is obtained until the subject fully completes her/his study participation of the study.

All AEs, whether believed by the Investigator to be related or unrelated to the investigational product, must be documented in the subject's medical records, in accordance with the Investigator's normal clinical practice and on the AE CRF. Each AE is to be evaluated for

duration, intensity, frequency, seriousness, outcome, other actions taken, and relationship to the investigational product.

12.1.4.2. Reporting of Serious Adverse Events

In agreeing to the provisions of this protocol, the Investigator accepts all legal responsibilities for immediate reporting of SAEs to the Sponsor. Immediate reporting implies within 24 hours of becoming aware of the occurrence of an SAE.

All SAEs must be reported to the Sponsor (including suspected liver-related clinical outcome events that qualify as serious).

SAEs are reported by entering the SAE data into the study-specific EDC system. Entering the SAE data into the EDC system will automatically notify the Sponsor of the event. In the event that the EDC system is inaccessible, an SAE may be reported by:

- E-mail to the SAE email address: [contact]
- Fax using a paper SAE report form: [contact]
- [contact]

If an SAE is reported by telephone or fax, an SAE Report form must also be completed in the EDC system as soon as the EDC system is accessible. At a minimum, the following information should be provided at the time of the initial report:

- Subject number
- Event term
- At least 1 criterion classifying the event as serious
- Name and title of the reporting individual
- Causal relationship to the investigational product

The Investigator will assess whether the event is causally related to the investigational product. The Sponsor will also assess whether the event is causally related to the investigational product, in addition to assessing the overall safety profile of the investigational product. The Sponsor will notify the appropriate regulatory agencies as well as all participating Investigators of Expedited Safety Reports that occur during the study within the time frames required by each regulatory agency.

Following the initial report, any additional information obtained by the Investigator about the SAE must be reported promptly to the Sponsor in the same manner as described above for the initial SAE report. Any supporting source documentation should be faxed to [contact] or emailed to [contact] as soon as possible. Redacted medical record source documentation will be requested for all SAEs and emergency room visits.

The Investigator is responsible for submitting information on Expedited Safety Reports received from the Sponsor to her/his local IRB/IEC, as directed by the local-country requirements. Documentation of the submissions to IECs/IRBs must be retained in the appropriate study file(s). As instructed by the Sponsor, Expedited Safety Reports should be retained in the appropriate investigative site study files or with the IB.

SAEs involving suspected liver-related clinical outcome events will be processed and reported by the Sponsor as described in Section 12.1.5.

12.1.5. Suspected Liver-Related Clinical Outcome Events

Specified liver-related clinical outcome events may, by definition (see [Section 12.1.1.2](#)) qualify as SAEs. The Sponsor must be notified of any SAEs within 24 hours of the site becoming aware of the event (see [Section 12.1.4.2](#)). The Sponsor is responsible for regulatory reporting of SAEs, including expeditious reporting of SUSARs, which are defined as SAEs that are considered related (definitely, probably, or possibly related) to the investigational product and considered unexpected as defined in the IB.

Given that the liver-related clinical outcome events could also meet the criteria of a SUSAR, which would necessitate unblinding for expedited reporting, the Sponsor will not expeditiously report suspected liver-related clinical outcome events in order to retain the study blind and preserve the integrity of the clinical outcomes endpoint. These events will be selected as a “study event” on the Adverse Event CRF and will be submitted for adjudication to the Hepatic Outcomes Committee as described in [Section 13.4](#).

The Sponsor will consider the following list of clinical outcome events (MedDRA preferred terms) to be disease related and exempt from expeditious regulatory reporting, but will continue to report them in a non-expeditious manner: death, end-stage liver disease (preferred term: chronic hepatic failure), liver transplant (preferred term: liver transplant), HCC (preferred term: hepatocellular carcinoma), variceal bleeding (preferred term: gastroesophageal variceal haemorrhage), hepatic encephalopathy (preferred term: hepatic encephalopathy), spontaneous bacterial peritonitis (preferred term: peritonitis bacterial), ascites (preferred term: ascites), and histological progression to cirrhosis (preferred term: hepatic cirrhosis).

12.1.6. Additional Investigator Responsibilities for SAEs

The safety data recorded in the CRF represent the official record of all AEs and SAEs reported in the study. The Investigator should comply with requests by the Medical Monitor or other Sponsor personnel to record the SAE on the subject’s AE CRF. Other supporting documents such as radiology reports, hospital discharge summaries, and autopsy reports should also be provided, when appropriate. Additionally, upon request by the Medical Monitor, the Investigator should provide input into the SAE narrative and provide timely information to ensure prompt follow up and closure of the SAE report.

The Investigator and supporting personnel responsible for subject care should discuss with the Medical Monitor any need for supplemental investigations of SAEs. The results of these additional assessments must be reported to the Medical Monitor.

12.1.7. Notification of Post-Study SAEs

If an Investigator becomes aware of an SAE that may be attributable to the investigational product at any time after the end of the study, the Sponsor should be notified immediately (ie, within 24 hours) by following the instructions provided in [Section 12.1.4.2](#).

All SAEs that occur within 30 days following the cessation of investigational product, whether or not they are related to the investigational product, must be reported to the Sponsor within 24 hours by following the instructions provided in [Section 12.1.4.2](#).

SAEs that occur more than 30 days after a subject has discontinued study medication, and are not considered related to investigational product, must still be reported in the EDC system; however, these events are not required to be reported within 24 hours. At a minimum, the SAE term, event start and end date, severity, relationship to investigational product, action taken with study medication, treatment, outcome, and potential endpoint status need to be recorded in EDC for the SAE. Additional information (e.g. event summary, SAE details) may also be required to be entered, when requested by the Sponsor.

